6. OBJECTIVES AND OUTCOME MEASURES

Objectives	Outcome Measures	Timepoint(s) of evaluation of this outcome measure (if applicable)
Primary Objective To compare the effect of the CMBT-S versus CBT plus standard psychopharmacotherapy for SPD.	
 Change in Personality pathology: Total score at PID-5-BF Schizotypal Personality Disorder Diagnosis: Diagnosis at the 3rd module of SCID-5-PD interview; General Psychopathology: Total score at SCL-90-R; Metacognition: Total score at MAS-A 	9 measurements: (i) at 1 month before intervention starts; (ii) once the treatment starts; (iii) 6 measurements at the end of each month of intervention; at 1-month follow-up; Pre-post evaluation between pre-assessment (1-month before the intervention) and 1-month follow-up assessment.
Secondary Objectives To assess the safety of CMBT-S in patients diagnosed with SPD	
 Dropout rate Completion rate Adverse events (suicidal behaviors, self-harm, psychotic episodes) rate 	At the end of the intervention: dropout rate ($\leq 10\%$ of subjects), completion rate ($\leq 10\%$ of sessions skipped), adverse event rate ($\leq 10\%$ of subjects).

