9.6. Early Discontinuation/Withdrawal of Participants

During the course of the trial a participant may choose to withdraw early from the trial treatment at any time. This may happen for a number of reasons, including but not limited to:

- The occurrence of what the participant perceives as an intolerable AE.
- Inability to comply with trial procedures
- Participant decision

Participants may choose to stop treatment and/or study assessments but may remain on study follow-up.

Participants may also withdraw their consent, meaning that they wish to withdraw from the study completely. Participants can withdraw completely from the study and withdraw the data and samples collected up until the point of withdrawal. The data and samples already collected would not be used in the final study analysis. (Any limits to this type of withdrawal where, for example analysis of their data or samples has already been integrated into interim results or dose escalation decisions etc. should be explained in the participant information sheet).

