11. SAFETY REPORTING

11.1. Adverse Event Definitions

Adverse Event (AE)	Any untoward medical occurrence in a participant to whom the intervention has been administered, including occurrences which are not necessarily caused by or related to that treatment.
Serious Adverse Event (SAE)	
A serious adverse event is any untoward medical occurrence that:
 
• results in death• is life-threatening• requires inpatient hospitalisation or prolongation of existing hospitalisation• results in persistent or significant disability/incapacity• consists of a congenital anomaly or birth defect*. 
Other 'important medical events' may also be considered a serious adverse event when, based upon appropriate medical judgement, the event may jeopardise the participant and may require medical or surgical intervention to prevent one of the outcomes listed above.
 
NOTE: The term "life-threatening" in the definition of "serious" refers to an event in which the participant was at risk of death at the time of the event; it does not refer to an event which hypothetically might have caused death if it were more severe.

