14.3. Trial committees

14.3.1 Safety Monitoring Committee

Tages Onlus will conduct a review of all SAEs for the trial reported during the quarter and cumulatively. The aims of this committee include:

- To pick up any trends, such as increases in un/expected events, and take appropriate action
- To seek additional advice or information from investigators where required
- To evaluate the risk of the trial continuing and take appropriate action where necessary

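### Section 9.6 removes withdrawn participants' data with no exception for adverse events, so the section 6 adverse event rate can be understated and harm reported as dropout

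*Combined protocol and SAP*

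**What the plan says.** The secondary objective in section 6 is "To assess the safety of CMBT-S in patients diagnosed with SPD". Its measures are the dropout rate, the completion rate and the rate of adverse events, the last defined as suicidal behaviours, self-harm and psychotic episodes. Each has a 10% limit, assessed once treatment is over, and the section words them as follows: "dropout rate ($\leq 10\%$ of subjects), completion rate ($\leq 10\%$ of sessions skipped), adverse event rate ($\leq 10\%$ of subjects". The denominator is given only as subjects.

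Section 9.6 describes three routes out:
- A participant may withdraw from trial treatment. The first reason listed is "The occurrence of what the participant perceives as an intolerable AE".
- A participant may stop treatment or assessments but remain in follow-up.
- A participant may withdraw consent altogether and "withdraw the data and samples collected up until the point of withdrawal". For this route, "The data and samples already collected would not be used in the final study analysis". A bracketed sentence adds that any limits to such withdrawal "should be explained in the participant information sheet". The protocol itself sets no limit.

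Section 12.1 bases the primary analyses on ITT and plans multiple imputation of scores for noncompleters. It defines no safety population and gives no rule for adverse events in people who withdraw. Under section 14.3.1 the sponsor will "conduct a review of all SAEs for the trial reported during the quarter and cumulatively".

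**The concern.** Of the three limits, only the adverse event rate measures harm directly. Dropout mixes poor tolerability with every other reason for leaving, and sessions skipped measures attendance. Read literally, section 9.6 takes a completely withdrawn participant's recorded self-harm or psychotic episode out of that one direct measure.

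The loss may depend on the outcome, because the event may be why the person left. For harmed participants, removal can only lower the rate. In an arm this small, one person decides whether the limit is met. At stake is a secondary safety result for a new therapy. The primary efficacy analysis is not part of this point.

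**Working it through.** **Inputs.** Total sample 14 (section 3); 1:1 allocation (section 7), hence 7 on CMBT-S; limits of 10% (section 6). The sample size is not in dispute. With f = 0.37, 9 measurements and correlation 0.50, lambda = 0.37² × 12 × 9 / (1 − 0.50) = 29.57 on 8 and 80 degrees of freedom. At alpha 0.05 (not stated, but implied by the critical F) this gives critical F 2.0564 and power 0.9786, as section 12.2 reports. Then 12/0.90 = 13.3, rounded up to 14.

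**Counts, CMBT-S arm of 7.**
- One harmed, data kept: 1/7 = 14.3%. Adverse event limit missed.
- Same patient withdraws completely with data: 0/6 = 0%. Adverse event limit met.
- If that withdrawal is counted as a dropout: 1/7 = 14.3%. Dropout limit missed.

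One event misses the limit in any arm of 9 or fewer (1/9 = 11.1%), so the example does not need an exact 7:7 split.

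**Counts, limits read over all 14.**
- Two harmed, data kept: 2/14 = 14.3%. Adverse event limit missed.
- One of the two withdraws completely with data: adverse events 1/13 = 7.7%, dropout 1/14 = 7.1%. Both limits met.

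**Probabilities.** These need two quantities that the documents do not give: the true adverse event risk a per patient, and the share w of affected patients who withdraw completely with their data. Both are assumed below, with patients independent, no other dropouts, and complete withdrawals counted as dropouts over all assigned patients.

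Arm of 7:
- The adverse event limit is met only if no counted event remains: P = (1 − a(1 − w))^7.
- Both limits are met only if there is no counted event and no withdrawal, that is, no event at all: P = (1 − a)^7, which does not contain w.

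All 14 (same risk a in both arms): enumerate h harmed and k withdrawn among them. The adverse event limit is met if (h − k)/(14 − k) ≤ 0.10, the dropout limit if k/14 ≤ 0.10.

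| a | w | AE limit met, n = 7 | Both met, n = 7 | AE limit met, n = 14 | Both met, n = 14 |
|---|---|---|---|---|---|
| 10% | 0 | 47.8% | 47.8% | 58.5% | 58.5% |
| 10% | 25% | 57.9% | 47.8% | 71.7% | 68.1% |
| 10% | 50% | 69.8% | 47.8% | 84.7% | 71.3% |
| 20% | 0 | 21.0% | 21.0% | 19.8% | 19.8% |
| 20% | 25% | 32.1% | 21.0% | 35.7% | 29.2% |
| 20% | 50% | 47.8% | 21.0% | 58.1% | 32.3% |

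The expected rate among patients left in the analysis is a(1 − w)/(1 − aw). At a = 20% it is 15.8% for w = 25% and 11.1% for w = 50%; at a = 10% it is 7.7% and 5.3%. With w = 0 there is no effect.

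**The case against.** The strongest reply is that the plan already catches the case. Dropout is a named safety measure with its own limit, and in a 7-patient arm a single complete withdrawal misses it. A reader who looks only at the adverse event column might infer that removal raises the chance of a favourable safety result from 21.0% to 47.8% (a = 20%, w = 50%). The documents do not support that: with the withdrawal counted as a dropout, the chance of meeting both limits stays at 21.0%. Only over all 14 does it rise, to 32.3% and not 58.1%, and that reading brings in CBT patients although the objective concerns CMBT-S. This reply stands. It leaves the understated adverse event rate in place, because a missed dropout limit does not tell anyone that self-harm occurred, and section 9.3 lets participants leave without giving a reason.

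Three further replies stand in part.
- A reader might infer that section 9.6 expects harmed patients to take their data with them. It does not: the intolerable event is a listed reason for leaving treatment, and withdrawing data is a separate option.
- The information sheet may already restrict data withdrawal. It was not available, so this cannot be ruled out; the protocol text sets no restriction.
- The sponsor's review would still see serious events. Section 11.1 includes events such as one that "requires inpatient hospitalisation or prolongation of existing hospitalisation" and leaves room for other important medical events by judgement. So harm need not disappear from view. But self-harm or a psychotic episode may fall short of serious, and nothing feeds that review back into the section 6 rate.

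**Conclusion.** The point holds as a minor one. As written, section 9.6 can understate the section 6 adverse event rate, and at this sample size one complete withdrawal by a harmed CMBT-S patient moves it from 14.3% to 0%, across the limit. In the 7-patient arm the consequence is that harm is reported as dropout. A false pass on both limits requires the 14-person reading, which section 6 leaves open by not naming the denominator.

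This rests on three assumptions: section 9.6 is applied literally, the information sheet adds no limit, and a complete withdrawal still counts as a dropout, which the plan does not say. How often it would happen is unknown; the values of a and w are illustrations.

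A reader might also conclude that safety should rest on the adverse event limit alone. The documents give no ground for that, and it would discard the limit that now catches the case.

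**What to change.** 1. State in section 9.6 and in the information sheet that adverse events recorded before withdrawal are kept in coded form (arm, type, date) and counted in the section 6 rate. The bracketed sentence in section 9.6 already provides for explaining such a limit.
2. In section 6, define the adverse event denominator as all CMBT-S participants who attended at least one session. Keep the dropout limit as a safety measure.
3. Where data must still be removed, for example for people who consented under the old text, report how many were removed and give the adverse event rate both without them and counting each as an event. With one removal from 7 and no other event, that is 0/6 = 0% to 1/7 = 14.3%. Present this as a sensitivity range, not a pass/fail rule: in a 7-patient arm the upper figure exceeds 10% after any removal, harmed or not.

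Cost: wording changes to sections 6 and 9.6, the information sheet and the consent form, submitted as an amendment under section 16.3; no new visits. The downside is that participants give up a small part of the right to have their data removed, which the ethics committee must approve.

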7. TRIAL DESIGN

Randomized Controlled Trial with Repeated Measures.

After being informed about the study and potential risks, all patients giving written informed consent will undergo a psychological assessment so as to determine eligibility for study entry. Patients who meet the eligibility requirements will be randomized in a double-blind manner in a 1:1 ratio to new integrative

psychotherapy or treatment as usual (cognitive behavioral therapy plus standard psychopharmacological treatment). One month after the conclusion of the two forms of treatment (both lasting 6 months), patients will have access to the final follow-up assessment.

8. PARTICIPANT IDENTIFICATION

8.1. Trial Participants

Participants with being diagnosed with Schizotypal Personality Disorder at SCID-5-AMPD with minimum age 18 years.

8.2. Inclusion Criteria

- Participant is willing and able to give informed consent for participation in the trial.
- Male or Female, aged 18 years or above.
- Diagnosed with Schizotypal Personality Disorder at SCID-5-AMPD.

8.3. Exclusion Criteria

The participant may not enter the trial if ANY of the following apply:

- Being under psychotherapy or psychopharmacological treatment
- Being diagnosed with schizophrenia and other psychotic disorders
- Being diagnosed with bipolar disorder
- Being diagnosed with intellectual disability
- Being diagnosed with any neurological diseases

9. TRIAL PROCEDURES

9.1. Recruitment

The recruitment centers were selected on the basis of their expertise in treating personality disorders and the presence of a multidisciplinary team. Subjects who during epidemiological studies or clinical assessment procedures report a diagnosis of SPD are approached and asked for their willingness to receive a subsequent assessment for possible entry into the study. Once the informed consent has been read and signed, the inclusion and exclusion criteria for the participants are confirmed. Finally, eligible subjects are randomized through software and assigned to treatment.

9.2. Screening and Eligibility Assessment

An assessment psychologist and a psychiatrist conduct an in-depth assessment of demographic and anamnestic variables and integrate them with the results of psychometric tests and structured interviews.

The maximum time between the assessment, the randomization and the start of the course is one month. Protocol waivers are not permitted.

9.3. Informed Consent

The participant must personally sign and date the latest approved version of the Informed Consent form before any trial specific procedures are performed.

Written and verbal versions of the Participant Information and Informed Consent will be presented to the participants detailing no less than: the exact nature of the trial; what it will involve for the participant; the implications and constraints of the protocol; the known side effects and any risks involved in taking part. It will be clearly stated that the participant is free to withdraw from the trial at any time for any reason without prejudice to future care, without affecting their legal rights and with no obligation to give the reason for withdrawal.

The participant will be allowed as much time as wished to consider the information, and the opportunity to question the Investigator, their GP or other independent parties to decide whether they will participate in the trial. Written Informed Consent will then be obtained by means of participant dated signature and dated signature of the person who presented and obtained the Informed Consent. The person who obtained the consent must be suitably qualified and experienced, and have been authorised to do so by the Chief/Principal Investigator. A copy of the signed Informed Consent will be given to the participant. The original signed form will be retained at the trial site.

9.4. Randomisation

A simple computer will generate random number for each participant. CRO will design the randomization schedule and will hold the allocation blind to all the investigators.

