3. SYNOPSIS

Trial Title	Compassion and Metacognition Based Therapy for Schizotypal Personality Disorder: A Pilot Non-inferiority Randomized Controlled Trial on Repeated Measures.
Internal ref. no. (or short title)	Compassion and Metacognition in Schizotypal Personality (CMBT).
Trial registration	Unique Protocol ID: 03-07072020
Sponsor	Tages Onlus [name]
Funder	N/A
Clinical Phase	Recruiting
Trial Design	Parallel Assignment Randomized Controlled Trial with Repeated Measures
Trial Participants	Minimum Age: 18 Years Being diagnosed with Schizotypal Personality Disorder at SCID-5-AMPD
Sample Size	14
Planned Trial Period	Total lenght: December 15, 2020 - December 20, 2021

	Pre-post evaluation between pre-assessment (1-month before the intervention) and 1 month follow-up.		
Planned Recruitment period	December 15, 2020 - September 30, 2021		
	Objectives	Outcome Measures	Timepoint(s)
Primary		Personality pathology: Total score at PID-5-BF	(i) at 1 month before intervention starts; (ii) once the treatment starts; (iii) 6 measurements at the end of each month of intervention; at 1-month follow-up.
Secondary		Schizotypal Personality Disorder Diagnosis: Diagnosis at the 3rd module of SCID-5-PD interview; General Psychopathology: Total score at SCL-90-R; Metacognition: Total score at MAS-A	Pre-post evaluation between pre-assessment (1-month before the intervention) and 1-month follow-up assessment.
Intervention(s)	
 IMP(s) nIMP(s) Other intervention(s) 	Compassion and Metacognition Based Therapy (CMBT): Third Wave Cognitive Therapy targeting metacognitive dysfunctions (through Metacognitively Oriented Psychotherapy) and selfcriticism (through Compassion Focused Therapy). 6-month therapy, including 24 weekly sessions.	
Comparator	Cognitive Behavioral Therapy: Standard Cognitive Behavioral Therapy for Personality Disorders plus Standard Psychopharmacological Treatment. 6-month therapy, including 24 weekly sessions.		

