12.2. Sample Size Determination

ANOVA: Repeated measures, within-between interaction has been conducted in order to a priori compute required sample size. As input we estimate ([name], 2020) an effect size f equal to 0.37 with a power $(1-\beta)$ equal to 0.95. Moreover, we considered 9 measurements with at least a correlation among them equal to 0.50 (PID-5-BF reports a test-retest value greater than 0.70). This led to a total sample equal to 12 (critical $F= 2.0563726$; actual power= 0.9785743). By considering at least 10% of withdrawal we

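### Section 9.4 states no restriction on the randomisation, and simple randomisation of 14 patients does not guarantee near-equal arms: if draws are independent, 9:5 or worse occurs in 42.4% of trials

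*Combined protocol and SAP*

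**What the plan says.** - **Method.** Section 9.4 (Randomisation): "A simple computer will generate random number for each participant". The next sentence gives the schedule to the CRO: "CRO will design the randomization schedule and will hold the allocation blind to all the investigators". The type of schedule is not described.
- **Order of events.** Section 9.1 (Recruitment) places consent and confirmation of eligibility first, after which "eligible subjects are randomized through software and assigned to treatment".
- **Ratio.** Section 7 (Trial Design) says that eligible patients "will be randomized in a double-blind manner in a 1:1 ratio".
- **Size.** Section 12.2 (Sample Size Determination) reports "This led to a total sample equal to 12" before withdrawals. The synopsis gives 14 as the planned number.

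Nowhere does the protocol mention blocks, a fixed count per arm, stratification or minimisation.

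**The concern.** One random number per participant, with no stated restriction, is the ordinary description of simple randomisation. In a large trial it gives nearly equal arms without further measures. With 14 patients it often does not.

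Three things are at stake:

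- **Very small arms.** A 9:5, 10:4 or 11:3 split leaves 5, 4 or 3 patients in one arm. Withdrawals and the per-protocol analysis in section 12.1 could reduce that arm further.
- **Robustness.** The repeated-measures ANOVA in section 12.1 tolerates unequal variances between arms less well when the arms differ in size. With so few patients in one arm, that assumption cannot be checked reliably.
- **Precision.** For a fixed total, the variance of the difference between arms is smallest when the arms are equal.

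**Working it through.** **1. The protocol's own figure.** The inputs from section 12.2 are f = 0.37, m = 9 measurements, correlation ρ = 0.50 and target power 0.95. Alpha is not stated; 0.05 is assumed, and it reproduces the stated critical F. For the within-between interaction with two equal groups:

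- λ = f²·N·m/(1−ρ), with degrees of freedom (m−1) and (N−2)(m−1).
- N = 12: λ = 0.1369 × 12 × 9/0.5 = 29.57; df 8 and 80; critical F 2.0564; power 0.9786. This matches the stated 2.0563726 and 0.9785743.
- N = 10: power 0.941, below 0.95, so 12 is the smallest even total that meets the target.
- Allowing for 10% withdrawal: 12/0.90 = 13.3, which rounds up to 14 with equal arms, as in the synopsis.

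The figure reproduces with the equal-groups formula.

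**2. How often simple randomisation gives unequal arms.** Assume 14 independent draws with probability 1/2 each. The number in one arm is Binomial(14, 0.5), with 2¹⁴ = 16,384 equally likely sequences. Both directions are counted.

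| Split | Sequences | Probability |
|---|---|---|
| 7:7 | 3,432 | 20.9% |
| 8:6 | 6,006 | 36.7% |
| 9:5 or worse | 6,946 | 42.4% |
| of which 10:4 or worse | 2,942 | 18.0% |
| of which 11:3 or worse | 940 | 5.7% |

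The first three rows sum to 16,384.

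**3. What the imbalance costs.** Relative efficiency against equal arms is 4·n₁·n₂/N². The variance of the difference between arms rises by its reciprocal. Power comes from multiplying λ by the same factor. With all 14 analysed, λ at 7:7 is 0.1369 × 14 × 9/0.5 = 34.50, with df 8 and 96 and critical F 2.0363.

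| Split | Relative efficiency | Variance increase | λ | Power |
|---|---|---|---|---|
| 7:7 | 1.000 | 0% | 34.50 | 99.3% |
| 8:6 | 0.980 | 2.1% | 33.80 | 99.2% |
| 9:5 | 0.918 | 8.9% | 31.68 | 98.7% |
| 10:4 | 0.816 | 22.5% | 28.16 | 97.4% |
| 11:3 | 0.673 | 48.5% | 23.23 | 93.6% |

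With only 12 analysed, the same scaling gives 96.0% at 8:4 and 91.8% at 9:3.

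**4. What restriction would change.** A list fixed at seven per arm gives 7:7 with certainty if all 14 enrol. Permuted blocks keep the arms close to equal even if recruitment stops early.

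**The case against.** The strongest reply is that the protocol never says the draws are independent. The CRO designs the schedule, and shuffled lists and permuted blocks are also built from computer random numbers. This stands as a limit: the percentages are conditional on the plain reading of section 9.4. It does not remove the point. If the list is restricted, the protocol should say so; if it is not, a better method is available from the same CRO.

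Three stronger readings are tempting, and the documents do not support them.

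- **That simple randomisation breaks the 1:1 promise.** Section 7 states a ratio, not a count of seven and seven. Equal assignment probability satisfies a 1:1 ratio in expectation. What is missing is a guarantee of near-equal arms.
- **That moderate imbalance leaves the trial underpowered.** A 10:4 split is worth 0.816 × 14 = 11.4 patients in equal arms, and a reader might set that against the 12 in section 12.2. But the target is power of 0.95, and 12 overshoots it at 0.979. With all 14 analysed, power at 10:4 is still 97.4%. It falls below 0.95 only at 11:3 or worse, which has probability 5.7%.
- **That imbalance is what prevents a judgement on the 10% safety criteria in section 6.** With no events, the one-sided 95% upper bound, 1 − 0.05^(1/n), is already 35% with 7 patients, against 53% with 4. Equal arms would not bring it near 10%. That limit comes mainly from the sample size.

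A further fair objection is that restriction costs predictability. In a block of 2, every second allocation is determined for anyone who knows the one before. In a shuffled 7 and 7 list, at least the last is determined. Section 9.5 describes participants, care providers and assessors as blinded, but the choice of list should not depend on nobody knowing earlier allocations. This cost is real and has to be managed.

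**Conclusion.** The point holds as a cheap design improvement. It is not a flaw that invalidates the trial. Section 9.4, read plainly, describes simple randomisation, and at N = 14 that leaves a 42.4% chance of 9:5 or worse and an 18.0% chance of 10:4 or worse. These figures assume 14 patients randomised and independent draws with probability 1/2.

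The effect on nominal power is small: from 99.3% at 7:7 to 97.4% at 10:4. This rests on the protocol's inputs (f = 0.37, nine measurements, correlation 0.50), an assumed alpha of 0.05, and all 14 patients analysed. The case for restriction therefore rests mainly on avoiding arms of 3 to 5 patients and on the robustness of the ANOVA, with a modest gain in precision. The loss of robustness to unequal variances is a qualitative argument here; it was not quantified.

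**What to change.** State in section 9.4 that the CRO prepares a restricted 1:1 list, in one of two forms:

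- one shuffled list of seven allocations to each arm; or
- permuted blocks with concealed, randomly varying sizes (for example 2 and 4), avoiding a list made up entirely of blocks of 2.

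The shuffled list gives exact balance if all 14 enrol. Blocks protect balance better if recruitment stops short. In either case, state that the list is held centrally and that each allocation is released singly, after consent and confirmed eligibility. The protocol already has the CRO holding the allocation and already places consent and eligibility before randomisation, so the new content is the restriction and the release of one allocation at a time. If the CRO's schedule is already restricted, the sentence need only say how, with block sizes kept in a document that investigators do not see.

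The cost is a sentence or two and possibly a different list from the same CRO, with no extra patients or visits. The downside is that some late allocations become predictable to anyone who knows the earlier ones. Concealed, varying block sizes and central release limit this but do not abolish it.
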